## 5. OUTCOME VARIABLES

All Aim 1 echocardiograms will undergo blinded review by a panel of 2 cardiologists (2012 WHF guidelines), consisting of pre-review by 2 of these cardiologists (to guide discussion) and final consensus determination by the panel. A side-by-side comparison of the echo done at the end of the GOAL Trial and the end of GOAL-Post will also be done. Echocardiograms will be reviewed with side-by-side two-year (completion of the GOAL Trial) and five-year (end of GOAL-Post) echocardiograms presented to the panel, with random right or left display. The panel will be blinded to timing of the echocardiograms and will determine if the studies were “the same”, “right worse” or “left worse” by application of strict operational definitions, defined in the GOAL Trial.

The primary outcome of **Aim 1** will be development of echocardiographic evidence of RHD (2012 WHF Criteria) among children and adolescents with a normal echocardiogram at the 2-year endpoint in the GOAL Trial and upon enrolment into GOAL-Post (variable enollecho).

An **alternative outcome** for **Aim 1** is worsening on a side-by-side comparison of the echo done at the end of the GOAL Trial and the end of the GOAL-Post trial. These will be assessed as same, progressed or regressed. This is done only for Group A. This is captured in the database as a combination of two variables. If eligible\_echo\_comparison is “no” then the result is “same”. If eligible\_echo\_comparison is “yes” then the result is captured in the variable side\_by\_side results. The final diagnosis is given as the variable final\_diagnosis\_after\_comparison. Again this variable is a combination of two variables . If eligible\_echo\_comparison is “no” then the result is “normal”.

The primary outcome of **Aim 2** will be echocardiographic progression and regression among children who had persistent latent RHD at the end of the GOAL Trial. This will be variable enollecho from Period 26.

Progression is defined as progression of echocardiographic features of latent RHD to include:

- New pathological regurgitation at a previously unaffected valve
- Worsening grade of existing mitral or aortic regurgitation (mild, moderate, severe)
- Development of two morphological features consistent with RHD (2012 WHF criteria) at a valve that previously had normal morphology or the addition of one morphological feature at a valve previously only showing a single morphological abnormality.

In all cases progression will involve a change in diagnostic category (borderline to definite mild, or definite mild to definite moderate/severe).

Regression will be defined as regression of echocardiographic features of latent RHD to include:

- Disappearance of existing mitral or aortic regurgitation, or change from pathological regurgitation to physiological regurgitation (2012 WHF criteria)
- Decreasing grade of existing mitral or aortic regurgitation (trivial, none)
- Disappearance of a morphological feature consistent with RHD (2012 WHF criteria) at a valve that previously had abnormal morphology.

In all cases, regression will involve a change in diagnostic category (borderline to normal, or definite to borderline/normal).

GOAL-Post	Statistical Analysis Plan
Version 1 – 2 July 2024	

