### **3.3. STUDY POPULATION**

**Aim 1** planned to enrol between 953 and 1102 participants, a maximum of 364 participants with normal echocardiograms after 2-years of participation in the GOAL Trial (Group A) and an appropriate number of age and sex matched controls (Group B, see sample size) without echocardiographic evidence of RHD.

**Group A:** Children and adolescents were eligible for Aim 1 if they

- (1) are a prior GOAL Trial participant deemed by the adjudication panel to have a normal echocardiogram at the 2-year endpoint,
- (2) are not receiving SAP, and
- (3) agree to participate in the study via the study's informed consent/assent process.

**Group B:** Children and adolescents were eligible for Aim 1 if they

- (1) have a normal echocardiogram at the start of the study,
- (2) meet the age and sex match requirement (from former GOAL Trial participants), and
- (3) have agreed to participate in the study via the study's informed consent/assent process.

**Aim 2** planned to enrol up to 415 participants with persistent latent RHD after 2 years of participation in the GOAL Trial. Children and adolescents were eligible for Aim 2 if they

- (1) were a prior GOAL Trial participant deemed by the adjudication panel to have persistent latent RHD on echocardiogram at the 2-year endpoint,
- (2) have been prescribed SAP (BPG), and
- (3) agree to participate in the study via the study's informed consent/assent process.

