## 4. POPULATIONS OF ANALYSIS

For **Aim 1** the analysis population will be all participants enrolled in Aim 1 in GOAL-Post. The Aim 1 Group A population is defined as GOAL-Post consent completed, arm 1 selected, and GOAL-Post enrolment echo is normal. The Aim 1 Group B population is defined as GOAL-Post consent completed and arm 4 selected.

For **Aim 2** the analysis population will be all participants enrolled in Aim 2 in GOAL-Post. The Aim 2 population is defined as GOAL-Post consent completed and arm 2 selected, or GOAL-Post consent completed, arm 1 selected, and GOAL-Post enrolment echo is not normal.

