## 6. STATISTICAL METHODOLOGY

### 6.1. AIM 1 PRIMARY ANALYSES

We will report the proportion of children who develop echocardiographic evidence of RHD in each of Group A and B (never diagnosed with latent RHD; negative at screening for GOAL, and negative when screened for GOAL-Post). We will fit a generalized linear model (GLM) with an identity link and binomial distribution, adjusted for the matching factors age and sex to estimate the difference in proportion of children who develop echocardiographic evidence of RHD, with a 95% confidence interval (CI), between Groups A and B.

To assess whether this difference in proportion between the two groups is < 2% we will evaluate the upper bound of the estimated 2-sided 95% CI for the difference in proportions calculated from the GLM. If this CI does not include a difference larger than 2%, the risk for development of RHD will be assessed to be similar in the two groups of participants.

Children with confirmed Acute Rheumatic fever (ARF) and children who develop echocardiographic evidence of RHD prior to the 2-year endpoint will be counted as having reached the primary study endpoint (development of RHD).

We will also repeat the analysis, using the same statistical methods, but restricting the analysis to only the subgroup of children who were randomized to the BPG arm in the GOAL Trial. This will reduce the sample size and power, therefore we do not expect to be powered to show statistically significant results, but will provide all estimates to serve for hypothesis generation.

The results of the side-by-side comparison of echocardiograms will be summarized.

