**Table 3: Aim 1 primary analysis**

Evidence of RHD	Proportion with RHD			
	Group A Proportion (95% CI)	Group B Proportion (95% CI)	Difference (95% CI)	p-value
All participants in Aim 1				
Only participants randomized to the BPG arm in the GOAL Trial				
Using side by side comparison				
All participants in Aim 1				
Only participants randomized to the BPG arm in the GOAL Trial				

Group A: Children who completed the GOAL Trial and have normal echocardiograms in GOAL-Post

Group B: A new group of age and sex matched controls who have normal echocardiogram at study entry

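### Table 3 calls for a Group A versus Group B difference on the side-by-side echo outcome, which is assessed only in Group A

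*SAP*

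**What the plan says.** SAP Section 5 has two layers of echo reading for Aim 1. First, a blinded panel reads all Aim 1 echocardiograms, in both groups, against the 2012 WHF criteria. This read gives the primary outcome.

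Second, the end-of-GOAL and end-of-GOAL-Post images are shown side by side, with left and right randomised. The SAP states: "The panel will be blinded to timing of the echocardiograms". This gives an alternative outcome (same, progressed or regressed), and the SAP adds: "This is done only for Group A".

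Not every pair is compared. A variable, `eligible_echo_comparison`, decides. For the comparison result, the rule is that if this variable "is “no” then the result is “same". For the final diagnosis, the rule is that if it "is “no” then the result is “normal". The SAP does not define when a pair is eligible.

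On analysis, Section 6.1 says: "The results of the side-by-side comparison of echocardiograms will be summarized". Table 4 then shows proportions progressed and regressed for Group A only. Table 3, however, contains a block headed "Using side by side comparison". Its two rows (all Aim 1 participants, and those randomised to BPG in GOAL) sit under the columns Group A, Group B, difference with 95% CI, and p-value.

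**The concern.** An outcome assessed in one group cannot supply a between-group difference. If the Table 3 cells are filled as laid out, a re-adjudicated Group A is set against a Group B that had only the ordinary panel read. A second look given to one group alone can shift that group's event count with no matching correction in the other. The resulting difference, interval and p-value would look like a supporting analysis of the primary question, when part of the difference could come from how the groups were ascertained.

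Two further consequences depend on the undefined eligibility rule. If eligibility means a non-normal final echo, the second look can move Group A's count in one direction only, towards a finding that the groups are similar. The same selection could also let a reader work out which image is the later one.

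**Working it through.** **1. Can Group B have this outcome?** It compares the end-of-GOAL echo with the end-of-GOAL-Post echo. In Section 3.5, Table 1, Group A uses its end-of-trial GOAL echo as baseline, while Group B has a full echo at the GOAL-Post enrolment visit. Group B therefore has no end-of-GOAL image to pair, which agrees with Section 5. The SAP names no other Group B value for these rows. The only one available is the ordinary panel read.

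**2. Do the places agree?**

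| Place in SAP | What it provides for |
|---|---|
| Section 5 | Side-by-side outcome in Group A only |
| Section 6.1 | A summary; no between-group model for this outcome |
| Table 4 | Group A proportions only |
| Table 3, side-by-side block | Group A, Group B, difference, p-value |

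Table 3 is the odd one out. This holds whatever the eligibility rule is.

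**3. What does the coding imply about eligibility?** A non-eligible pair receives a final diagnosis of normal. A child with a non-normal final echo must therefore be eligible, or an RHD case would be recorded as normal. The converse does not follow: nothing says that a pair with a normal final echo is never eligible. That only non-normal final echoes are compared is thus an inference.

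**4. What follows if the inference is right?** Every Group A child starts normal. Section 3.3 requires a child "deemed by the adjudication panel to have a normal echocardiogram at the 2-year endpoint", and Section 4 defines the group by "arm 1 selected, and GOAL-Post enrolment echo is normal". Each compared pair would then consist of an earlier image read as normal and a later one read as non-normal. The comparison could confirm or withdraw the RHD call. It could not add one, because all other children are coded as unchanged without being compared.

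**5. Size, on that reading.** The SAP gives no rate of withdrawal, so there is no planned figure to reproduce. Inputs from Section 3.4: at most 364 in Group A, 10% loss, 3% assumed risk.

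- Completers: 364 × 0.9 = 327.6, about 328.
- Expected Group A events: 0.03 × 328 = 9.8, about 10.
- Shift in the difference per withdrawn event: 1/328 = 0.30 points.
- Assumed number withdrawn, 1 to 5: 1/328 = 0.30, 3/328 = 0.91, 5/328 = 1.52 points.

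At the SAP's smallest Group A, 291 enrolled gives 291 × 0.9 = 262 completers, and the shift per event is 1/262 = 0.38 points.

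**6. Blinding.** If a reader knew the selection rule and saw only Group A pairs, the abnormal image would be recognisable as the later one, and random left or right display would not hide that. The SAP does not say what the panel knows about selection or how pairs are batched.

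**The case against.** The strongest reply is that the eligibility variable is undefined, so a one-way effect is not established. If some pairs with a normal final read are also compared, the second look could add events. Table 4 even has a row for Group A children who regressed, which would be close to empty if every compared pair ran from normal to abnormal. That row may be template text, but it counts against treating the inference as fact. This objection stands, and the direction and size above are therefore conditional.

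A reader might also infer that the timing blinding is void. The documents do not support that. Section 6.2 and Table 6 make the side-by-side result the primary outcome of Target-GOAL, which includes children with latent RHD at two years, whose pairs can regress. If those pairs are read in the same sessions, image order is not deducible. The SAP neither states nor excludes such mixing, so the most that can be said is that blinding may be weakened.

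Finally, a reader might set the shift against the 2-point margin and conclude that the main result is at risk. It is not. The margin in Section 6.1 belongs to the primary outcome, which rests on a panel read applied to both groups. The side-by-side result is an alternative outcome with no margin or decision rule, and the number withdrawn is an assumption.

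None of this supplies a Group B value for Table 3.

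**Conclusion.** The point holds for the Table 3 layout. The side-by-side block asks for a between-group difference, interval and p-value on an outcome that Section 5 confines to Group A, and it conflicts with Section 6.1 and Table 4. Any number placed there would compare groups ascertained in different ways. This rests on the text alone.

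The lean towards similarity is conditional on eligibility being limited to non-normal final echoes. It would then be 0.30 points per withdrawn event at 328 completers, or 0.3 to 1.5 points for an assumed 1 to 5 withdrawals. Possible weakening of the timing blinding is conditional on the same reading and also on what the panel knows and how pairs are batched. The issue should be corrected, but it concerns a non-primary outcome.

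**What to change.** - In Table 3, delete the two side-by-side rows, or mark Group B, difference and p-value as not applicable there.
- Report the side-by-side result for Group A only, as descriptive, in Table 4. This matches Section 6.1.
- In Section 5, define `eligible_echo_comparison`, and say plainly that non-eligible pairs are assigned `same` and `normal` without comparison.
- In Section 5, describe the blinding to timing as possibly limited by that selection, and say how pairs are batched for reading, including whether Target-GOAL pairs are mixed in.

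The cost is SAP wording and two table rows. No new readings are needed.

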## 6. STATISTICAL METHODOLOGY

### 6.1. AIM 1 PRIMARY ANALYSES

We will report the proportion of children who develop echocardiographic evidence of RHD in each of Group A and B (never diagnosed with latent RHD; negative at screening for GOAL, and negative when screened for GOAL-Post). We will fit a generalized linear model (GLM) with an identity link and binomial distribution, adjusted for the matching factors age and sex to estimate the difference in proportion of children who develop echocardiographic evidence of RHD, with a 95% confidence interval (CI), between Groups A and B.

To assess whether this difference in proportion between the two groups is < 2% we will evaluate the upper bound of the estimated 2-sided 95% CI for the difference in proportions calculated from the GLM. If this CI does not include a difference larger than 2%, the risk for development of RHD will be assessed to be similar in the two groups of participants.

Children with confirmed Acute Rheumatic fever (ARF) and children who develop echocardiographic evidence of RHD prior to the 2-year endpoint will be counted as having reached the primary study endpoint (development of RHD).

We will also repeat the analysis, using the same statistical methods, but restricting the analysis to only the subgroup of children who were randomized to the BPG arm in the GOAL Trial. This will reduce the sample size and power, therefore we do not expect to be powered to show statistically significant results, but will provide all estimates to serve for hypothesis generation.

The results of the side-by-side comparison of echocardiograms will be summarized.

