## 2. STUDY OBJECTIVES

### 2.1. PRIMARY OBJECTIVE

To assess whether children who completed the GOAL (GwokO Adunu pa Lutino, “protect the heart of a child”) Trial and now have normal echocardiograms have the same risk for progression as a new group of age and sex matched controls who have a normal echocardiogram at study entry.

**Aim 1:** Compare the two-year risk of echocardiographic progression between children and adolescents who completed the GOAL Trial with a normal echocardiogram (that is, a prior diagnosis of latent RHD) and age and sex matched controls with repeated normal echocardiograms (normal in both the original GOAL screening in 2017/2018 and in the GOAL-Post screening in 2021).

**Hypothesis:** The risk of RHD development (2012 World Heart Federation [WHF] Criteria) in children and adolescents who have had normalization of their echocardiogram following latent RHD diagnosis is not higher than children and adolescents without prior documentation of latent RHD.

**Clinical application:** We are trying to answer the question: “Is it safe to take these children off Benzathine Penicillin G (BPG) after two years if they do not show latent RHD?”

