### **3.2. TREATMENT GROUPS**

The following treatment groups are identified within GOAL-Post:

- Never diagnosed with latent RHD (negative at screening for GOAL, and negative when screened for GOAL-Post) – Group 1B. This group has never received SAP.
- Randomized in the GOAL Trial to SAP and normal echocardiogram (no latent RHD) at the 2-year endpoint of the GOAL Trial and at the start of GOAL-Post. (Children who had SAP for two years and are then taken off SAP given a normal echocardiogram and no sign of latent RHD.)
- Randomized in the GOAL Trial to SAP and latent RHD at the start of GOAL-Post.
- Randomized in the GOAL Trial to control and normal echocardiogram (no latent RHD) at the 2-year endpoint of the GOAL Trial and at the start of GOAL-Post, these participants never received SAP.
- Randomized in the GOAL Trial to control and latent RHD at start of GOAL-Post. These participants did not receive SAP in the GOAL Trial but did receive SAP in GOAL-Post.

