### **3.4. SAMPLE SIZE**

**Aim 1:** A sample size of between 953 and 1102 participants (up to 350 and as few as 291 participants with normal echocardiograms after the GOAL Trial and up to 811 age and sex matched controls) will be needed, assuming up to 10% loss to follow-up and that 2% of the control group (Group B), and 3% of the children who completed the GOAL Trial (Group A) will develop RHD.

A two-group large-sample normal approximation test of proportions with a one-sided 2.5% significance level will have 80% power to reject the null hypothesis of a difference in proportions of <2% in favor of the alternate hypothesis that the proportion of the two groups are equivalent. Calculation was done using nQuery 8 (Statistical Solutions Ltd). This sample size was increased by 10% to account for loss to follow-up.

GOAL-Post	Statistical Analysis Plan
Version 1 – 2 July 2024	

**Aim 2** does not include a comparator group and will include the maximum number of former GOAL Trial participants with persistent latent RHD (currently 415 retained in care).

For Aim 1 Group A we plan to enrol all the participants who were enrolled in the GOAL Trial, meet the eligibility criteria and are willing to be enrolled in the GOAL-Post extension study. The maximum number that can be enrolled in group A is 364 who had normal echocardiograms at the end of the GOAL Trial. If this maximum number is enrolled, and there is 10% loss to follow-up in GOAL-Post, we need to enrol 589 participants in Group B. This gives a total sample size of 953.

Since there is only a fixed number of children who qualify for enrolment into Group A, we determined the size of Group B after group A has been enrolled. The size of Group B was determined to give 80% power, given the size of Group A, under the previous assumptions. The smallest sample size for Group B is given above. If 90% of the original cohort are enrolled in Group A, the size of Group A will be 328 and the size of Group B will be 666 for a total sample size of 994. If only 80% of the original cohort are enrolled in Group A, the size of Group A will be 291 and the size of Group B will be 811 for a total sample size of 1102.

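### SAP section 6.1 does not fix the interval type, age coding or fallback for the 2% decision. If Wald limits are used, the unadjusted false-claim rate at true risks of 4% v 2% is 3.9–5.0%, not 2.5%

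*SAP*

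**What the plan says.** SAP section 6.1 sets out the primary model for Aim 1: "We will fit a generalized linear model (GLM) with an identity link and binomial distribution, adjusted for the matching factors age and sex". The conclusion rests on one number from it: "we will evaluate the upper bound of the estimated 2-sided 95% CI for the difference in proportions calculated from the GLM". The rule follows: "If this CI does not include a difference larger than 2%, the risk for development of RHD will be assessed to be similar".

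Section 3.4 gives the operating characteristics the decision is meant to have: "A two-group large-sample normal approximation test of proportions with a one-sided 2.5% significance level will have 80% power". The assumed risks are "2% of the control group (Group B), and 3% of the children who completed the GOAL Trial (Group A) will develop RHD", with 10% loss to follow-up. The planned enrolments (Group A / Group B) are 364/589, 328/666 and 291/811.

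Neither section, nor any other part of the plan, names the type of confidence limit, says how age enters the model, or says what is done if the fit does not converge or a fitted risk reaches zero.

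**The concern.** A Wald limit and a profile-likelihood limit can both fairly be described as calculated from the GLM. Two analysts who follow section 6.1 to the letter could therefore compare different upper limits with 2%. With risks of 2–4% and about 300 children in Group A, the two limits are not interchangeable. The Wald limit tends to be too low here, and the resulting error is the unsafe one: the risks are called similar when Group A is truly 2 points worse.

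Section 2.1 gives the clinical question as "Is it safe to take these children off Benzathine Penicillin G (BPG) after two years if they do not show latent RHD". The Aim 1 comparison informs that question. If the interval, the age coding and the fallback are settled only after the data are seen, the level stated in section 3.4 no longer describes the test.

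**Working it through.** **Inputs (SAP 3.4 and 6.1).** Margin 2 points for A minus B; two-sided 95% limit, i.e. "one-sided 2.5% significance level"; risks A 3%, B 2%; 10% loss. Completers are 90% of enrolment: 364/589 → 328/530, 328/666 → 295/599, 291/811 → 262/730.

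**1. The plan's own group sizes.** The unpooled normal-approximation formula for Group B given Group A is

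nB = pB(1−pB) / { [(0.02 − (pA−pB)) / (1.960+0.842)]² − pA(1−pA)/nA }.

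- At the stated A 3%, B 2% with nA = 327.6, the bracket squared is (0.01/2.802)² = 0.0000127, which is less than 0.0291/327.6 = 0.0000888. No Group B size gives 80% power. At the planned sizes the same approximation gives 13–14%.
- At A 2%, B 3%: 0.0291 / (0.0001147 − 0.0000598) ≈ 531 completers, or 589.6 enrolled. The other two sizes come to 669.8 and 811.8.

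The planned sizes are thus reproduced, closely, only with the two rates exchanged. That is a separate problem and the present point does not depend on it, but power is shown below at both pairs of rates.

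**2. Expected events in Group A.** At the planned 3%: 328, 295 and 262 × 0.03 = 9.8, 8.8 and 7.9. At 4%, where the false-claim rate is evaluated: 13.1, 11.8 and 10.5.

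**3. False-claim rate, exact and unadjusted.** Sum Bin(x; nA, pA) × Bin(y; nB, pB) over all pairs (x, y) whose upper limit is below 0.02, with pA − pB = 0.02. With d the observed risk difference, the limit is below 0.02 when:

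- Wald: d + 1.96·√[p̂A(1−p̂A)/nA + p̂B(1−p̂B)/nB] < 0.02.
- Profile likelihood: d < 0.02, and twice the log-likelihood drop from the unrestricted fit to the fit restricted to a difference of 0.02 exceeds 1.96².
- Miettinen-Nurminen score: (d − 0.02)/√V < −1.96, where V uses the restricted risks and the factor N/(N−1), N being total completers.

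| True risks | Limit | 328/530 | 295/599 | 262/730 |
|---|---|---|---|---|
| A 4%, B 2% | Wald | 3.9% | 4.4% | 5.0% |
| | Profile | 2.8% | 3.1% | 2.8% |
| | Score | 2.1% | 1.8% | 1.8% |
| A 3%, B 1% | Wald | 5.0% | 5.3% | 6.3% |

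At A 5%, B 3% the Wald rate is 3.6–4.6%.

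**4. How often the choice matters.** At the stated A 3%, B 2%, Wald and profile give different decisions in 4.2%, 4.6% and 6.9% of datasets for the three sizes. An example picked at the boundary is 8/328 v 14/530: d = −0.20 points, standard error 1.10, Wald upper limit −0.20 + 1.96 × 1.10 = 1.95%. The profile limit is 2.16% and the score limit 2.32%, so only Wald meets the margin.

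**5. Adjustment and boundary fits (simulation, illustrative).** The plan gives no age distribution, so ages were assumed, with sex 1:1.

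- Wald error at A 4%, B 2% among fits away from the boundary was about 5.6–5.9% with linear age and 6.2–6.7% with three bands. Adjustment does not obviously remove the excess.
- At A 3%, B 2% and no age effect, the best valid fit had a zero risk in 20–27% of datasets with linear age and uniform ages, 33–42% with bell-shaped ages, and 12–20% with two bands.
- With single-year age categories at A 4%, B 2%, about 99% of fits lay on the boundary.

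**The case against.** **The plan never says Wald.** This stands. A reader might infer that the plan as written has a 5% error. The documents do not support that: the 3.9–5.0% is conditional on Wald and unadjusted, while section 6.1 specifies an adjusted model. The normal approximation in section 3.4 describes the sample-size calculation and does not name the decision interval.

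**The interval type seldom matters at the planned rates.** Largely right. At the counts expected under plan (10/328 v 11/530, 9/295 v 12/599, 8/262 v 15/730) the Wald limits are 3.2–3.3%, and every method fails the margin. The example that changes decision has Group A slightly below Group B and is not near plan. Only a borderline result is affected.

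**The analysis can still be run.** A reader might infer from the boundary fits that it cannot. That goes too far: a constrained maximum-likelihood estimate exists even at a zero risk, and how often this happens depends on ages the plan does not give. What is undefined there is the interval.

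**The comparison does not by itself settle whether stopping prophylaxis is safe.** Correct. Group A also holds GOAL controls with a normal echocardiogram, of whom section 3.2 says "these participants never received SAP" (there the abbreviation means secondary antibiotic prophylaxis).

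**Profile likelihood also exceeds 2.5%.** True, slightly, which is why it is the second choice below.

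**Conclusion.** The point holds as under-specification of a decision rule. Three choices that can settle a borderline Aim 1 result are open. If the usual default, Wald, fills the first of them, the unadjusted chance of wrongly calling the risks similar is 1.6 to 2.0 times the stated level (3.9/2.5 to 5.0/2.5) at true risks of 4% and 2%.

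The unadjusted figures are exact for independent binomial counts at the planned sizes after 10% loss. They would shift with other background risks. The adjusted and boundary figures rest on assumed ages and show direction only. The point should be corrected but is secondary to the mismatch between rates and group sizes in section 3.4, because at the rates as stated the margin is rarely met by any method.

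**What to change.** **Preferred.** State in section 6.1 that the 2% decision uses the upper limit of a two-sided 95% Miettinen-Nurminen score interval for the risk difference, stratified by sex and a few prespecified age bands. The GLM estimate and its Wald interval become supportive. This keeps the adjustment for the matching factors and needs no data-dependent switch of method. In simulations with assumed ages its error was 1.7–2.1%.

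**If the GLM is kept for the decision.** Name its profile-likelihood limit, with age in prespecified bands and fitted risks held within 0 and 1. Name the stratified score interval as the single fallback if the fit fails or a fitted risk reaches 0 or 1. Accept an error near 2.5%, not strictly below it (2.2–3.0% in the same simulations with two bands).

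Either way, recheck the error at the margin with the enrolled age and sex distribution before the analysis.

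**Cost.** Wording, standard software and lower nominal power. Exact unadjusted power over the three sizes:

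| True risks | Wald | Profile | Score |
|---|---|---|---|
| A 2%, B 3% (reproduce the group sizes) | 77–79% | 68–74% | 61–69% |
| A 3%, B 2% (as stated) | 18–19% | 12–14% | 9–11% |

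Part of the Wald advantage comes only from exceeding the stated error level.
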